### 5.2 Intent-to-Treat Sample

As the primary analysis, all efficacy and safety outcome measures will be analyzed under the intent-to-treat principle (ITT). Under this principle, the evaluable sample includes all subjects who are randomized (regardless of what treatment was actually

received). Each subject will be analyzed according to the treatment group to which they were randomly assigned at the time of randomization.

It should be noted that the role of the ITT population in a non-inferiority trial is not equivalent to that of a traditional superiority trial. The traditional role tends to dilute the treatment effect in favor of no difference between groups; however in the non-inferiority setting this dilution may favor the non-inferiority hypothesis. Therefore the definition of ITT for a non-inferiority trial needs to take into account the impact of missing data on the primary outcome as well as that of non-compliance. For the SVI Trial, non-compliance of the indomethacin alone arm is anticipated to be rare due to the mode of delivery (rectal) and the one-time nature of this intervention. Non-compliance of the combination arm may occur if the endoscopist cannot place the stent however we anticipate this to be minimal. Both of these events are anticipated to be rare (no more than 5%). Missing primary outcome data is also anticipated to be rare with the expectation of minimal loss to follow up due to our brief 30-day follow-up period. Scenarios in which it may occur are if the subject cannot be reached and/or hospital records cannot be obtained. In the event of either of these scenarios, the primary outcome will be imputed (refer below to Handling of Missing Data Section).

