At the time of each planned analysis (interim and final), the unblinded statistician will report the amount of missing primary outcome data. If there is 5% or less missing primary outcome data, then all missing cases (regardless of treatment arm) will be considered worse case scenario (i.e., having a PEP event). If there is more than 5% missing data, then multiple imputation using SAS PROC MI and MIANALYZE will be used to impute the primary outcome. We chose 5% as our threshold for missing data due to the fact that the performance of the various imputation methods has negligible differences when the amount of missing data is small. In summary, 5 imputed data sets will be generated using PROC MI. The imputation model will include the primary analysis variables (PEP event, treatment) plus age and gender. Each imputed data set will be analyzed according to the specified primary analysis (Section 10.1.2) and MIANALYZE will be used to combine the results from the multiple imputed data sets to obtain a single set of parameter estimates. The multiple imputation method assumes missing at random (MAR) which means that the probability of missing outcome data can depend on the observed values of the individual but not on the missing values of the individual. Although we anticipate minimal missing data, sensitivity analyses will be conducted to assess the impact of any bias due to missing data. The final primary analysis will be re-run using complete case analysis (only those with outcome). If the treatment effect is robust, we expect these sensitivity analyses to yield similar inferences, particularly if the missing data are minimal (~5%). Any discrepancies between the sensitivity analyses and the primary analysis results will be investigated to understand the reason for the discrepancy.

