**9.3 Secondary Outcome Variable Analysis**

Analysis of the secondary outcome, the proportion of subjects with moderate-severe PEP, will be analyzed in a similar manner as the primary outcome.

We also will examine the impact of pre-specified characteristics on the primary and secondary outcomes. Specifically, the goal of this analysis is to examine prognostic variables and their impact on the primary analysis. We also will explore subgroup populations for future hypothesis generation. The baseline variables that will be examined are: age (continuous), gender, race, body mass index (continuous), suspicion of sphincter of Oddi dysfunction, prior post-ERCP pancreatitis, history of recurrent pancreatitis, manometrically documented sphincter of Oddi dysfunction, difficult cannulation, pre-cut (access) sphincterotomy, pancreatic sphincterotomy, pancreatic acinarization, biliary sphincterotomy, pancreatic stent placement, double wire technique, make/model/length/caliber of pancreatic stent, trainee involvement, prophylactic stent characteristics, type of sphincter of Oddi dysfunction, and inpatient vs. outpatient status. The assessment of each of these variables will be conducted using a logistic regression model with the dichotomous primary outcome, PEP event. Treatment arm will be a main effect in the model and the above covariates examined. Each covariate will be assessed individually first with a model that includes interaction effect with the treatment. If a significant interaction is observed ( $p < 0.10$ ), then exploratory subgroup analyses will be considered. For each model, we will be looking at the parameter estimate of the covariate to examine its association with outcome. We also will be examining the parameter estimate of the treatment in the presence of the covariate. A multivariable model will be created based on the results of the individual models (a combination of statistical and clinical significance will be used for model inclusion). The final multivariable model will be based on goodness of fit criteria. For this final model, the adjusted risk difference will be estimated with a 95% confidence interval. If the upper limit of this confidence interval is 5% or greater, then non-inferiority of the treatments cannot be concluded in the presence of the particular covariates. This analysis will be run on both the ITT and PP analysis populations.

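### In the ITT fits of the SAP 9.3 prognostic models, scoring missing outcomes as PEP biases the covariate associations; no stated 9.3 model uses all randomised subjects with an observed outcome

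*SAP*

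**What the plan says.** SAP 9.3 states that "the goal of this analysis is to examine prognostic variables and their impact on the primary analysis". Each listed covariate is assessed "using a logistic regression model with the dichotomous primary outcome, PEP event", with treatment in the model, first singly with a treatment interaction and then in a multivariable model. An interaction at p < 0.10 can lead to exploratory subgroup work. The final model yields an adjusted risk difference that is judged against the 5% margin. On populations, the section says "This analysis will be run on both the ITT and PP analysis populations".

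SAP 5.2 makes ITT (all randomised subjects, as assigned) the primary basis for every efficacy measure and provides for imputation of missing primary outcomes. SAP 8 gives the rule: "If there is 5% or less missing primary outcome data, then all missing cases (regardless of treatment arm) will be considered worse case scenario", which the SAP spells out as having a PEP event. Beyond that threshold, "If there is more than 5% missing data, then multiple imputation using SAS PROC MI and MIANALYZE will be used", with an imputation model holding only PEP, treatment, age and gender. The complete-case re-run in SAP 8 is stated for the final primary analysis alone.

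SAP 5.4 removes eligibility violations, treatment crossovers and missing primary outcomes from the per-protocol sample.

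**The concern.** Scoring every missing case as an event in both arms is a choice about the risk difference between arms. A prognostic model asks something else: which patients develop pancreatitis. There, the same coding makes being unreachable, or having unobtainable records, part of the outcome.

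Two distortions follow. If missingness is unrelated to a factor, its odds ratio moves towards 1. If missingness differs across a factor's levels, a factor unrelated to PEP can appear to predict it. Inpatient versus outpatient status is on the 9.3 list and could plausibly be linked to how easily records are obtained.

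These estimates help select covariates for the multivariable model, can prompt subgroup exploration, and supply the association between the risk score and PEP. SAP 9.3 says that the prognostic results will be taken into account in interpreting the trial.

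**Working it through.** **Does the rule reach these models?** The 9.3 outcome is the primary PEP variable. The population is ITT, ITT imputes missing outcomes, and 9.3 sets no exception. On the natural reading the scored events enter. If the population sentence is read narrowly, as covering only the final adjusted model, SAP 5.2 still places the single-covariate models under ITT.

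**Inputs.** PEP rates *p* of 9.7% (design rate, SAP 4.2) and 13% (suggested threshold for raising the sample size, SAP 4.3); maximum N of 2,180; 5% ceiling for the scoring rule (SAP 8). Assumed, because the documents give no figures: missing fractions *m* of 1% and 2%, a 10% baseline risk, a true odds ratio of 2.0, and the differential splits below. The plan gives no imputed share of its own to reproduce.

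**Step 1: share of modelled events that are imputed**, m / [m + (1 − m)p], with *p* the rate among subjects with an outcome.

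| Missing | p = 13% | p = 9.7% |
|---|---|---|
| 1% | 0.01/0.1387 = 7.2% | 0.01/0.1060 = 9.4% |
| 2% | 0.02/0.1474 = 13.6% | 0.02/0.1151 = 17.4% |
| 5% | 0.05/0.1735 = 28.8% | 0.05/0.1422 = 35.2% |

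At N = 2,180 and 5% missing there are 109 scored events, against about 201 observed events at 9.7% or 269 at 13%.

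**Step 2: share falsely coded.** Some missing subjects may truly have had PEP. If they have it at the same rate as the others, multiply by (1 − p). At the ceiling, 35.2% × 0.903 = 31.8% and 28.8% × 0.87 = 25.1%.

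**Step 3: attenuation when missingness is unrelated to the factor.** Each risk becomes p′ = (1 − m)p + m. A 10% baseline with odds ratio 2.0 means risks of 0.100 and 0.1818.
- m = 1%: 0.109 and 0.190, odds ratio 0.2346/0.1223 = 1.92
- m = 2%: 0.118 and 0.198, odds ratio 0.2472/0.1338 = 1.85
- m = 5%: 0.145 and 0.223, odds ratio 0.2866/0.1696 = 1.69

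**Step 4: spurious association for a factor unrelated to PEP.** With two levels of equal size, the splits below average 2% and 5% missing, so the scoring rule applies.
- 3% v 1% missing: at p = 13%, risks 0.1561 v 0.1387, odds ratio 1.15; at 9.7%, 0.1241 v 0.1060, odds ratio 1.19
- 8% v 2% missing: at p = 13%, 0.1996 v 0.1474, odds ratio 1.44; at 9.7%, 0.1692 v 0.1151, odds ratio 1.57

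**Step 5: is there an unaffected version?** The per-protocol fit has no imputed events, but it also loses crossovers and eligibility violations. The complete-case re-run covers the primary analysis only. No stated 9.3 model therefore uses all randomised subjects with an observed outcome.

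**The case against.** The strongest reply is that the effect will probably be small. The SAP says "Missing primary outcome data is also anticipated to be rare". Its roughly 5% sample-size allowance covers drop-in, drop-out and missing data together. The outcome arises within 2 days and is taken from hospital records; the protocol plans a contact at days 3–5 and obtains permission for outside records at consent. A reader might infer from the 5% ceiling that about a third of the modelled events will be loss to follow-up. The documents do not support that as an expectation. It needs missingness right at the switch point together with the 9.7% design rate, whereas the sample size was raised because a higher rate was observed. At 13% the ceiling is 29%, and at 1% missing the share is 7–9%.

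A reader might also infer that the risk score is built on contaminated outcomes. It is not: SAP 9.3 fixes the points in advance (1 per major criterion, 0.5 per minor). Only the score's estimated association with PEP is affected.

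The per-protocol run is a real safeguard, and non-compliance is expected to be no more than 5%. But if the ITT and per-protocol fits differ, the reader cannot tell whether the scored outcomes or the other exclusions caused it.

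Finally, moving everything in 9.3 to observed outcomes would go too far. It would mix covariate adjustment with a change in missing-data handling in the adjusted risk difference, alter the site-stratified interval, and displace multiple imputation above 5%. That objection stands, and the fix is limited accordingly.

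**Conclusion.** The concern holds for the covariate associations in the ITT fits of SAP 9.3. Its size depends on the missing fraction: slight at 1% (odds ratio 2.0 read as about 1.92), moderate at 2% (1.85), and material at 5% (1.69). The attenuation is in a known direction when missingness is unrelated to the factor. Spurious odds ratios of 1.15–1.19 or 1.44–1.57 rest on the assumed 3% v 1% and 8% v 2% splits; the documents give no data on differential missingness.

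This is a secondary-analysis point. It does not show that the primary non-inferiority comparison is biased: that analysis is unadjusted and has its own complete-case check. The change is worth making because it is cheap, not because the trial's conclusion depends on it.

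**What to change.** In SAP 9.3, state that when 5% or less of primary outcomes are missing, the single-covariate, interaction, covariate-selection and risk-score association estimates use all randomised subjects with an observed primary outcome, by assigned arm.

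Keep the adjusted risk difference and the site-stratified Newcombe interval under the primary missing-data rule, each with an observed-outcome version as sensitivity. Keep the per-protocol run.

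Above 5% missing, keep multiple imputation but add the 9.3 covariates to the imputation model. As written it omits most of them, so their associations would still be diluted. For example, with an assumed 6% missing, 10% baseline risk and a factor present in half the subjects, missing cases are imputed at the average risk of 0.1409. The risks become 0.94 × 0.100 + 0.06 × 0.1409 = 0.1025 and 0.94 × 0.1818 + 0.06 × 0.1409 = 0.1794, and an odds ratio of 2.0 becomes about 1.91.

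The cost is a short SAP edit. Subjects without an outcome (at most 5% in this branch) leave the prognostic models, and the adjusted risk difference is reported under two missing-data treatments.

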8.2.4 Randomization

During the procedure, when one or more inclusion criteria have been met AND it has been determined that none of the exclusion criteria are present, AND the papilla (major or minor depending on indication) has been visualized and deemed accessible, the subject will be randomized to receive a 100 mg of rectal indomethacin (two 50mg suppositories) only or the combination of PSP and 100 mg of rectal indomethacin in a 1:1 fashion using a web-based electronic randomization system that will be accessed on a computer within the endoscopy suite. The randomization schedule will be generated centrally at the data coordinating center and will ensure treatment balance within site.

NOTE: SUBJECTS NOT MEETING ANY INCLUSION CRITERIA OR IDENTIFIED AS INELIGIBLE BASED ON EXCLUSION CRITERIA DURING THE ERCP WILL NOT BE RANDOMIZED.

- Subjects in whom the consent process is initiated but are not consented will be recorded in the Screen Failure Log along with the reason for eligibility exclusion or unwillingness to provide consent.
- Consented subjects who are not randomized will be recorded in the Screen Failure Log along with the reason for eligibility exclusion.
- Consented subjects not eligible for randomization will receive continued medical treatment per standard of care at each institution and appropriate details will be documented in the subject research record.

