## **6. RANDOMIZATION**

A web-based central randomization system will be developed by the SDMC and installed on the WebDCU™ SVI study website using a minimal sufficient balance randomization scheme with a 1:1 allocation ratio. Baseline site imbalance will be controlled at the minimal sufficient level so that there will not be serious treatment imbalance within site. The randomization algorithm will be fully detailed and documented in the SVI Randomization Plan and Validation Documents. These documents will be developed prior to the enrollment initiation and stored in a secure location at the SDMC. The documents will be archived with the study database at the end of the trial. Subjects, study coordinators and the adjudicators will all be blind as to which treatment was received. Subjects will not be told of their actual treatment until the Trial completion unless emergency unblinding is required. This information will be accessible in the event of an emergency via an emergency unblinding procedure (see MoP for further details).

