For the multivariable model, it is possible that several of the baseline characteristics will be eligible for the model. In this case, we will derive a risk score based on the methods used in the previous indomethacin trial. Individual patient risk scores will be determined by assigning one point for each major inclusion criteria and 0.5 points for each minor inclusion criteria (see below table). Similar to the above methods, the derived risk score will be examined for inclusion in the final multivariable model. In addition to the risk score, we will use a propensity score approach to derive a baseline variable that describes the baseline risk. The results of each risk score approach will be compared to provide helpful information for future trials.

Major Risk Criteria (1pt each)	Minor Risk Criteria (0.5pts each)
Suspicion of SOD	Age < 50
Prior post-ERCP pancreatitis	Female gender
Difficult cannulation	History of recurrent pancreatitis
Pre-cut sphincterotomy	
Pancreatic sphincterotomy	

Several procedures have been incorporated into the study design (i.e., procedure manual, training, protocol violation monitoring, outcome adjudication) to reduce center effects; however, these effects should not be ignored for this trial. As a secondary analysis of the study outcomes, a two-sided confidence interval for the difference in the PEP event rate between the two treatment arms will be calculated using the Newcombe method, stratifying by site. Non-inferiority will be concluded if the upper limit of the confidence interval is less than 5%. Similar to the assessment of potential prognostic variables, the results of this secondary analysis will be taken into account when interpreting the final results of the trial.

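### SAP 9.3 names a propensity score as a second measure of baseline PEP risk, but in a 1:1 randomised trial that score models the arm, not PEP, and ranks risk no better than chance

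*SAP*

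**What the plan says.** SAP 9.3 examines covariates one at a time "using a logistic regression model with the dichotomous primary outcome, PEP event" and then builds a multivariable model. If several characteristics qualify, it condenses them into a points score: "Individual patient risk scores will be determined by assigning one point for each major inclusion criteria", and half a point for each minor one. The table lists five major and three minor items.

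Beside this it places a second measure: "we will use a propensity score approach to derive a baseline variable that describes the baseline risk". The next sentence treats the two as rivals for the same task: "The results of each risk score approach will be compared to provide helpful information for future trials".

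For the second measure the SAP does not state the modelled outcome, the covariates, any validation, or whether the variable enters the final model. Neither document gives the term propensity score a special meaning.

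On allocation, SAP 6 describes a central system "using a minimal sufficient balance randomization scheme with a 1:1 allocation ratio" and adds: "Baseline site imbalance will be controlled at the minimal sufficient level". Protocol 8.2.4 says that the schedule "will be generated centrally at the data coordinating center and will ensure treatment balance within site". No PEP risk factor is described as entering the algorithm.

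The list of baseline variables in SAP 9.3 includes "pancreatic stent placement, double wire technique, make/model/length/caliber of pancreatic stent, trainee involvement".

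**The concern.** A propensity score answers the question of which arm a patient was likely to receive. A measure of baseline risk answers how likely the patient was to develop PEP. In observational data the two can be related, because sicker patients are steered to one treatment. Randomisation removes that link on purpose.

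An analyst who follows the text would fit a model for arm and label the result baseline risk. Comparing it with the points score would then set a risk measure against noise, and whichever looked better would tell future trials nothing. What is at stake is that comparison and the second risk measure.

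**Working it through.** The SAP gives no figure for this score, so there is none to reproduce. The check has four steps.

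**1. The true score.** Let e(X) = P(indomethacin alone | X), where X holds covariates fixed before randomisation. Allocation is 1:1 (SAP 6, Protocol 8.2.4). The balancing step responds to arm counts within a site, not to patient risk, and favours neither arm overall. Hence e(X) = 0.5 for high-risk and low-risk patients alike.

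**2. The fitted score.** With K covariates unrelated to arm and N subjects, the fitted model explains by chance a share of about K/N of the variance of the arm indicator, which is 0.5 × 0.5 = 0.25. So SD ≈ 0.5 × √(K/N). N is the original or the revised maximum sample size. K is assumed, because the SAP does not list the covariates; 8 happens to match the number of items in the points table (5 + 3). The last two columns come from 200 simulated trials per setting.

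| N | K | 0.5 × √(K/N) | Simulated SD | 1st to 99th percentile |
|---|---|---|---|---|
| 1430 | 8 | 0.037 | 0.036 | 0.42 to 0.58 |
| 1430 | 15 | 0.051 | 0.049 to 0.050 | 0.39 to 0.61 |
| 2180 | 8 | 0.030 | 0.029 | 0.44 to 0.56 |
| 2180 | 15 | 0.041 | 0.040 to 0.041 | 0.41 to 0.59 |

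The scatter is what chance imbalance alone produces.

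**3. Does the score rank PEP risk?** Suppose PEP rates are equal in the two arms, as the sample size calculation assumes (SAP 4.2). Swapping the arm labels is then equally likely and turns a fitted score e into 1 − e, and a c-statistic c into 1 − c. The expected c-statistic is therefore 0.50, whatever the strength of the risk factors.

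The simulations used a PEP rate of 9.7% (SAP 4.2). Further assumptions, because the documents do not give these inputs, were binary factors with prevalence 10% to 50% and an odds ratio of 1.5 or 2.0 each.

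- Score fitted to arm: mean correlation with true risk −0.04 to 0.06; mean c-statistic for PEP 0.49 to 0.52. In single trials the central 95% of c-statistics reached, at the extremes across settings, from about 0.32 to 0.68. In one trial the score is as likely to rank risk backwards as forwards.
- Score fitted to PEP on the same covariates: in-sample c-statistic 0.65 to 0.80, against 0.64 to 0.79 for the true risk.

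Other assumptions give the same picture. With N = 2180, PEP 15% and five modest factors (300 trials), the arm score had SD 0.023 (formula: 0.5 × √(5/2180) = 0.024) and a c-statistic of 0.50. A cross-validated PEP score reached about 0.63 (0.58 to 0.68 for weaker or stronger factors).

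**4. If stent placement entered the score.** Assume 95% placement in the combination arm and 2% in the other; both rates are assumptions. With equal arms:

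- P(indomethacin alone | stent) = 0.02 / (0.02 + 0.95) = 0.021
- P(indomethacin alone | no stent) = 0.98 / (0.98 + 0.05) = 0.951

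One simulated data set of 2180 gave 0.019 and 0.959. The score now identifies the arm almost perfectly and still says nothing about the risk the patient brought to the procedure.

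**The case against.** The strongest reply is that the SAP never says that arm is the modelled outcome. The sentence speaks of baseline risk, the next one calls the result a risk score approach, and the other logistic models in SAP 9.3 have PEP as outcome. The authors may well have meant a regression-based risk score for PEP. That is plausible, and on that reading the score would not be empty. But the SAP would then name the wrong method and leave the intended one undefined. Both readings need the same correction.

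A second reply is that adjusting for a fitted propensity score in a randomised trial is legitimate, because it deals with chance imbalance. That is true, but it is not the purpose stated here.

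A third reply is that little hangs on it, and this stands. The primary difference is not adjusted for covariates (SAP 9.1). The risk-score step is introduced for the case in which several characteristics qualify. Only the points score is expressly considered for the final model.

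Two stronger readings are tempting. A reader might infer that the trial loses its risk modelling; it does not, since the points score and the multivariable PEP model do not depend on this sentence. A reader might also infer that the covariate-adjusted risk difference, which SAP 9.3 sets against the 5% margin, is compromised. The documents do not support that, because they give the propensity variable no role in that model.

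**Conclusion.** As written, SAP 9.3 names a method that cannot measure baseline PEP risk. With covariates fixed before randomisation the true score is 0.5, a fitted score reflects chance imbalance, and its expected c-statistic for PEP is about 0.50. With the stent variables included it would mostly reproduce the arm. It would therefore be too strong to say that every patient's score is about 0.5: that holds for the true score on pre-randomisation covariates, while fitted values scatter around it.

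The conclusion rests on the standard meaning of propensity score and on the allocation described in both documents. It does not rest on the simulated risk-factor strengths. The c-statistics for a PEP-based score do depend on those assumptions and are illustrations, not predictions for this trial.

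Severity is low. The damage is confined to the secondary, exploratory comparison of risk-score approaches; the primary non-inferiority conclusion is unaffected.

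**What to change.** Replace the propensity score approach in SAP 9.3 with a prognostic (disease-risk) score and specify:

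- **Outcome and model:** logistic regression with PEP as the outcome.
- **Covariates:** a named list of variables determined before randomisation, excluding prophylactic stent placement and stent characteristics.
- **Validation:** internal, for example by cross-validation, so that the score is not judged only on the data that produced it.
- **Comparison:** discrimination (c-statistic) and calibration, against the points score.

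No new data or software is needed. The cost is a short SAP revision and a little more analysis work. The main task is to sort the SAP 9.3 list into variables settled before and after randomisation. That takes some care, because Protocol 8.2.4 places randomisation during the procedure and several listed items arise during the same procedure.
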